7.7.3. Rescue Medicine

Use of medications that may impact efficacy evaluations is strongly discouraged at any time after Visit 1 in the study. However, participants who experience severe symptoms of GP after entering the Treatment Period or RWP, may receive a single day of treatment per week with an anti-emetic drug, but should avoid such treatment, if possible, on the day prior to and day of clinic visits during the Treatment Period. If a participant requires an anti-emetic drug (eg, 5-HT3 receptor antagonists, NK1 receptor antagonists) for more than 1 day a week, or requires an anti-emetic drug once weekly repeatedly (ie, for 3 consecutive weeks or more), the investigator should contact the sponsor to discuss the safety of the participant continuing in the study.

The date of rescue-medication administration as well as the name and dosage regimen of the rescue medication should be recorded in the concomitant medications page of the eCRF.

7.8. Treatment after the End of the Study

Participants who complete the study should follow up with the investigator regarding treatment at the end of the study

8. Discontinuation/Withdrawal Criteria

Reasons for discontinuation from study treatment and/or the study may include the following:

- Adverse event
- Completed
- Death
- Lack of efficacy
- Lost to follow-up
- Other
- Investigator or physician decision
- Pregnancy
- Protocol deviation

Relamorelin

- Site terminated by sponsor
- Study terminated by sponsor
- Withdrawal by participant

The reason for discontinuation should be clearly documented on the appropriate eCRF. Discontinuation of study treatment also requires discontinuation from the study.

(See [Appendix 8](#) for Standard Discontinuation Criteria/Definitions.)

8.1. Discontinuation of Study Treatment

Discontinuation of study treatment also requires discontinuation from the study. [REDACTED]

[REDACTED]

[REDACTED]

Relamorelin

8.1.1. Temporary Discontinuation

[figure not shown]
In the event of AE or intercurrent illness, dosing of study treatment can be stopped temporarily, for a maximum duration of 3 days. Should longer cessation of dosing be necessary, the investigator should contact the sponsor. The investigator should also contact the sponsor should either recurrence of the AE that prompted discontinuation or the appearance of a new AE that requires discontinuation be experienced after reintroduction of treatment to discuss the safety of this participant continuing study.

8.2. Withdrawal from the Study

- A participant may withdraw from the study at any time at his/her own request, or may be withdrawn at any time at the discretion of the investigator for safety, behavioural, compliance, or administrative reasons. An early termination visit must be performed as soon as possible after the decision to withdraw has been made by the participant or the decision to withdraw the participant has been made by the investigator.
- If the participant withdraws consent for disclosure of future information, the sponsor may retain and continue to use any data collected before such a withdrawal of consent.
- If a participant withdraws from the study, he/she may request destruction of any samples taken and not tested, and the investigator must document this in the site study records.
- See the SoA (Section 2) for data to be collected at the time of study discontinuation.

8.3. Lost to Follow-up

A participant will be considered lost to follow-up if he or she repeatedly fails to return for scheduled visits and is unable to be contacted by the study site.

9. Study Assessments and Procedures

- Study procedures and their timing are summarized in the SoA (Section 2).
- Protocol waivers or exemptions are not allowed.
- Safety concerns should be discussed with the sponsor immediately upon occurrence or awareness to determine if the participant should continue or discontinue study treatment.
- Adherence to the study design requirements, including those specified in the SoA, is essential and required for study conduct.

9.1. Efficacy Assessments

9.1.1. Key Efficacy Assessment – DGSSD

The primary efficacy assessment is the DGSSD, a 7-item, patient-reported daily diary designed to assess the severity of 6 core signs and symptoms of DG—nausea, abdominal pain, postprandial fullness, bloating, vomiting, and early satiety ([Appendix 13](#)) and the frequency of vomiting episodes.

DGSSD entries are to be made daily at the same time every evening on the electronic hand-held device during the 12-week period before Visit 4 of the Treatment Period, the 4-week periods before Visits 5, 6, and 7 of the Treatment Period, and throughout the 6 weeks of the

Relamorelin

Randomized-withdrawal Period. Planned timepoints for all efficacy assessments are provided in the SoA (Section 2).

The severity of DG symptoms is assessed using a 0 to 10 numerical rating scale (NRS), on which 0 = “no” or “not at all uncomfortable” (ie, absence of the DG symptom) and 10 = “worst possible” or “most uncomfortable” (ie, worst experience of the DG symptom).

[figure not shown]
An overall assessment of the severity of non-vomiting symptoms is derived from the weekly DGSSS, which is the sum of the weekly averages of DGSSD items of nausea, abdominal pain, postprandial fullness, and bloating. Weekly assessments are calculated from a participant’s daily DGSSD responses.

The DGSSS ranges from 0 to 40, with the worst possible DGSSS for the 4 DG symptoms being 40, and the best possible DGSSS being 0. Psychometric analyses have shown that a decrease in the DGSSS by ≥ 10 points and a decrease in individual symptom scores by ≥ 2 points is recognized as a clinically meaningful improvement in DG symptoms by affected patients ([Psychometric Evaluation, RTI Health, 2017](#)).

Vomiting frequency will be captured daily on the electronic hand-held device. Participants will be asked to indicate the number of vomiting episodes experienced in the day since the previous entry made, with information to be provided as to what constitutes a “vomiting episode” in order to ensure accurate reporting. Vomiting is defined as throwing up the contents of the stomach. This does not include retching or dry heaving (also known as dry vomiting) when no stomach contents are thrown up.

Weekly assessment of vomiting frequency is derived as the normalized total number of vomiting episodes during a week. This is defined as:

Weekly normalized number of vomiting episodes = (total number of vomiting episodes in the week) * (7 days / [number of days with non-missing responses in the week])

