- Study Duration: 46 weeks, consisting of a 40-week Treatment Period followed by a 6-week RWP:
 - 40-week Treatment Period: Participants who meet entry criteria at the end of either lead-in study RLM-MD-01 or RLM-MD-02 will continue to receive the same blinded treatment with relamorelin 10 µg or placebo that they received during the lead-in study Treatment Period. They will continue to use the electronic hand-held device for reporting of [REDACTED] compliance and rescue-medication use throughout the Treatment Period, and for completion of the Diabetic Gastroparesis Symptom Severity Diary (DGSSD) daily during the first 12 weeks (84 days) of the Treatment Period until Visit 4 and during each 4-week period before Visits 5, 6 and 7.

Relamorelin

- 6-week RWP: At the end of the 40-week Treatment Period, participants who were on relamorelin will be randomized (1:1) either to continue relamorelin study treatment or switch to placebo study treatment. Participants who received placebo during the Treatment Period will be allocated to receive relamorelin 10 µg. Participants will continue to use the electronic hand-held device daily for reporting of their symptoms via the DGSSD as well as their compliance, and use of rescue medication.

Figure 1-1 RLM-MD-03 Study Schematic

Number of Participants:

Approximately 960 participants, based on assumption that 80% of participants who enter lead-in study RLM-MD-01 or lead-in study RLM-MD-02 will complete the study and enter this study.

Relamorelin

Study Population:*Key Inclusion Criteria:*

1. Participant met all inclusion/exclusion criteria of either Protocol RLM-MD-01 or Protocol RLM-MD-02 and successfully completed the study
2. Able to provide written informed consent (IC) prior to any study procedures and willing and able to comply with study procedures
3. In the opinion of the investigator, the participant demonstrated adequate compliance with the study procedures in RLM-MD-01 or RLM-MD-02

Key Exclusion Criteria:

1. Participant is not willing or able to abide by the restrictions regarding concomitant medicine use
2. Participant is planning to receive an investigational drug (other than study treatment) or investigational device at any time during Study RLM-MD-03
3. Participant has an unresolved AE or a clinically significant finding on physical examination, clinical laboratory test, or 12-lead ECG that, in the investigator's opinion, would limit the participant's ability to participate in or complete the study

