5.1. Overall Design

[figure not shown]
- Global, multicenter, double-blind, placebo-controlled, parallel-group
- Treatment Groups: Relamorelin 10 μg or placebo; BID, SC
- Study Duration: 46 weeks
- Study Periods:
 - 40-Week Treatment Period: Participants who meet entry criteria at the end of either lead-in study RLM-MD-01 or RLM-MD-02 will continue to receive the same blinded treatment with relamorelin 10 μg or placebo that they received during the Treatment Period of the lead-in study and continue to use the electronic hand-held device for the first 12 weeks (84 days) of the Treatment Period as they did in the lead-in study for daily reporting of their symptoms via the Diabetic Gastroparesis Symptom Severity Diary (DGSSD) as well as [REDACTED] compliance, and use of rescue medication. After Day 84 (Visit 4), participants will continue daily reporting of compliance and use of rescue medication, but will report their symptoms via the DGSSD, [REDACTED] only during the 4 weeks preceding subsequent visits (Visit 5 through Visit 7 or Early Termination).

Relamorelin

- 6-Week RWP: At the end of the 40-week Treatment Period, participants who were on relamorelin will be randomized (1:1) either to continue relamorelin study treatment or switch to placebo study treatment. Participants who received placebo during the Treatment Period will be allocated to receive relamorelin 10 µg. Participants will continue to use the electronic hand-held device daily for reporting of their symptoms via the DGSSD as well as their compliance, and use of rescue medication.

See Figure5-1 for a Study Schematic.

Figure 5-1 RLM-MD-03 Study Schematic

Study Population:

Participants who successfully complete lead-in study RLM-MD-01 or lead-in study RLM-MD-02 and meet enrollment criteria for this study shall constitute the study population. Their 40-week treatment assignment will have been determined by randomization during the lead-in study.

Relamorelin

For studies conducted at US (IND) sites and non-US (non-IND) sites, data from IND and non-IND study sites will be pooled together for analysis.

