3. MACE

Serious AESIs should be reported to the sponsor within 24 hours via the SAE form.

Relamorelin

Events Meeting the AE Definition

- Any abnormal laboratory test results (hematology, clinical chemistry, or urinalysis) or other safety assessments (eg, ECGs, radiological scans, vital signs measurements), including those that worsen from baseline, considered clinically significant in the medical and scientific judgment of the investigator (ie, not related to progression of underlying disease)
- Exacerbation of a chronic or intermittent pre-existing condition including either an increase in frequency and/or intensity of the condition
- New condition detected or diagnosed after study treatment administration even though it may have been present before the start of the study
- Signs, symptoms, or the clinical sequelae of a suspected drug-drug interaction
- Signs, symptoms, or the clinical sequelae of a suspected overdose of either study treatment or a concomitant medication. Overdose per se will not be reported as an AE/SAE unless it is an intentional overdose taken with possible suicidal/self-harming intent. Such overdoses should be reported regardless of sequelae.
- Lack of efficacy or failure of expected pharmacological action per se will not be reported as an AE or SAE. Such instances will be captured in the efficacy assessments. However, the signs, symptoms, and/or clinical sequelae resulting from lack of efficacy will be reported as AE or SAE if they fulfill the definition of an AE or SAE.

Events NOT Meeting the AE Definition

- Any clinically significant abnormal laboratory findings or other abnormal safety assessments that are associated with the underlying disease, unless judged by the investigator to be more severe than expected for the participant's condition
- The disease/disorder being studied or expected progression, signs, or symptoms (clearly defined) of the disease/disorder being studied, unless more severe than expected for the participant's condition
- The following events are considered to be manifestations of diabetic gastroparesis and will be captured in the DGSSS but they will not be reported as AEs or SAEs: nausea, abdominal pain, upper abdominal pain, vomiting, postprandial fullness, bloating, and early satiety.

Relamorelin

If the investigator considers these manifestations to have a reasonable possibility of relationship to the study treatment/device(s) then they should be reported as AEs or SAEs.

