4.1 Study Design

Approximately 960 participants will enter this study at 700 study sites (globally), based on the assumption that 80% of participants who complete the lead-in pivotal registration studies RLM-MD-01 or RLM-MD-02 will elect to continue receiving the double-blind study treatment. Approximately 480 participants to receive relamorelin and 480 participants to receive placebo for an additional 40 weeks in the Treatment Period, and 6 weeks in the subsequent randomized withdrawal period (RWP). In the RWP, participants who received relamorelin in the Treatment Period will be re-randomized 1:1 to either continue relamorelin or switch to placebo; participants who received placebo in the Treatment Period will all switch to relamorelin.

Study Duration: 46 weeks, consisting of a 40-week Treatment Period followed by a 6-week RWP:

- 40-week Treatment Period: Participants who meet entry criteria at the end of either lead-in study RLM-MD-01 or RLM-MD-02 will continue to receive the same blinded treatment with relamorelin 10 µg or placebo BID that they received during the Treatment Period of the lead-in study and continue to use the electronic hand-held device for the first 12 weeks (84 days) of the Treatment Period as they did in the lead-in study for daily reporting of their symptoms via the Diabetic Gastroparesis Symptom Severity Diary (DGSSD) as well as their [REDACTED] compliance, and use of rescue medication. After Visit 4/Week 12, participants will continue daily reporting of compliance and use of rescue medication, but will report their symptoms via the DGSSD, [REDACTED] only during the 4 weeks preceding subsequent visits (Visit 5/Week 24 through Visit 7/Week 40 or Early Termination).
- 6-week RWP: At the end of the 40-week Treatment Period, participants who were on relamorelin will be randomized (1:1) either to continue relamorelin treatment or switch to placebo BID treatment. Participants who received placebo during the Treatment Period will be allocated to receive relamorelin 10 µg BID. Participants will continue to use the electronic hand-held device daily for reporting of their symptoms via the DGSSD as well

as their [REDACTED]
compliance, and use of rescue medication.

Study schematic and schedule of evaluations for Study RLM-MD-03 are presented in Figure 4.1–1 and Table 4.1–1 respectively.

Figure 4.1–1. RLM-MD-03 Study Schematic

[figure not shown]
[figure not shown]
[figure not shown]

Table 4.1–1. Schedule of Activities: Study RLM-MD-03

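### Seven gastrointestinal symptoms are kept out of AE reporting because the symptom score is said to capture them, but the diary is off for at least 16 of 40 treatment weeks and throughout the 30-day AE follow-up

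*Protocol*

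**What the plan says.** **The exclusion.** Protocol Section 12.4.1 lists seven symptoms as manifestations of diabetic gastroparesis: the four DGSSS symptoms plus upper abdominal pain, vomiting and early satiety. It says that these "will be captured in the DGSSS but they will not be reported as AEs or SAEs". Three other provisions of the same section bear on this:

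- A listed symptom with a reasonable possibility of relationship to the treatment or device is to be reported.
- The general bullet on symptoms of the disease under study excepts those more severe than expected.
- Exacerbation of a pre-existing condition, in frequency or intensity, is listed as an AE.

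Section 12.4.2 adds that an event which is not an AE cannot be an SAE, and gives hospitalisation for symptoms of the disease under study as an example.

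**The diary.** Section 9.1.1 schedules DGSSD entries "during the 12-week period before Visit 4 of the Treatment Period, the 4-week periods before Visits 5, 6, and 7 of the Treatment Period", and then throughout the RWP. Section 5.1 says that after Day 84 symptoms are reported "only during the 4 weeks preceding subsequent visits (Visit 5 through Visit 7 or Early Termination"), while "participants will continue daily reporting of compliance and use of rescue medication". SAP Section 4.1 repeats the schedule and dates it as "Visit 5/Week 24 through Visit 7/Week 40 or Early Termination".

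**The AE window.** Section 9.2.1 collects AEs until 30 days after Visit 8 or the Early Termination visit.

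**The score and the diary differ.** The DGSSS is "the sum of the weekly averages of DGSSD items of nausea, abdominal pain, postprandial fullness, and bloating". The DGSSD is the wider instrument: it also records vomiting severity, early satiety and the number of vomiting episodes.

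**The concern.** Leaving expected disease symptoms out of AE reporting is a usual choice when another instrument records them. Here that condition is the stated reason for the exclusion, and the protocol's own schedule does not meet it for a large part of the long-term phase.

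This matters because nausea, vomiting and abdominal pain are target symptoms and can also be signs of harm or of lost effect. Protocol Section 12.6 itself counts nausea and vomiting among the symptoms in its liver criteria. The study's purpose is to assess long-term treatment, and Section 5.4 cites a recommendation for a 12-month placebo-controlled safety study. The gap falls wholly in that long-term part.

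The SAP does not close it. SAP Section 11 bases safety on AEs, laboratory tests, ECG and vital signs, with no safety summary of diary symptoms. SAP Section 11.1 tabulates TEAEs by system organ class and preferred term. A reader of those tables would take a low rate of vomiting or abdominal pain as what was observed, although a reporting rule partly produces it.

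**Working it through.** The documents state no count of off-diary weeks, so there is no figure of the plan's own to reproduce.

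**Inputs**

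- Length: "40-week Treatment Period followed by a 6-week RWP" (protocol synopsis).
- Diary periods: 12 weeks before Visit 4, 4 weeks before each of Visits 5, 6 and 7, and all 6 weeks of the RWP (protocol Sections 5.1 and 9.1.1).
- Visit weeks: Visit 4 = Week 12, Visit 5 = Week 24, Visit 7 = Week 40 (SAP Section 4.1). The week of Visit 6 is not in the readable text, so it was varied.

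**Step 1: diary weeks in the Treatment Period.** If no blocks overlap, diary weeks = 12 + 3 x 4 = 24, and off-diary weeks = 40 - 24 = 16.

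- 16 x 7 = 112 days
- 16/40 = 40% of the Treatment Period
- 16/28 = 57% of Weeks 13-40

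**Step 2: sensitivity to Visit 6.** With Visit 6 placed at each week from 25 to 40:

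- Weeks 28 to 36: 16 off-diary weeks.
- Weeks 25 to 27, or 37 to 40: blocks overlap and the count is 17 to 20.

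So 16 is the minimum. If Visit 6 is at Week 32 (an assumption), the off-diary weeks are 13-20, 25-28 and 33-36.

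**Step 3: after Visit 8.** Diary entries end with the RWP and AE collection runs 30 days longer. Those days come on top of the 16 weeks.

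**Step 4: the seven symptoms against the two instruments**

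- Not in the DGSSS: vomiting, early satiety, and upper abdominal pain as a separate item.
- Not in the DGSSD: only upper abdominal pain as a separate item.

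While the diary is on, it therefore collects vomiting and early satiety. Naming the DGSSS is a wording error and does not itself lose data.

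**Step 5: where a listed symptom is recorded if judged unrelated and as expected**

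| Period | Diary | AE/SAE |
|---|---|---|
| Weeks 1-12 | yes | no |
| 4-week blocks before Visits 5, 6, 7 | yes | no |
| At least 16 other weeks, all after Week 12 | no | no |
| RWP | yes | no |
| 30 days after Visit 8 | no | no |

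The gap is the two rows with no entry in either column. A 4-week diary block before an unplanned Early Termination cannot be relied on to fill it, because the date is not known in advance.

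**The case against.** The strongest reply is that the exclusion is far from absolute. Possibly related symptoms must be reported, symptoms more severe than expected are excepted, and exacerbation counts as an AE. Signs and symptoms resulting from lack of efficacy are also reportable if they meet the AE definition. This stands, and it narrows the gap to symptoms judged both unrelated and as expected. It does not close the gap. Those judgements are left to individual investigators, and the seven-symptom bullet does not say how it fits with the exacerbation and severity provisions beside it, so two sites could treat the same event differently.

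Three stronger readings are tempting, and the documents do not support them:

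- *New daily vomiting in, say, Week 16 would necessarily go unrecorded.* Such a change could be reported as an exacerbation, as more severe than expected, or as possibly related. It is lost only if none of these is invoked.
- *Vomiting and early satiety are never captured because the DGSSS omits them.* The DGSSD collects both while it is on, and SAP Section 15.2 derives weekly values for them.
- *Worsening that leads to withdrawal between diary blocks leaves no trace.* Rescue use is reported daily and entered in the eCRF (protocol Sections 5.1 and 7.7.3). Lack of efficacy is a recorded reason for discontinuation (Section 8), and reasons are summarised by arm (SAP Section 7). An early termination visit is required (Section 8.2). These records are indirect, but they exist.

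The statement in Section 9.1.1 that vomiting frequency is captured daily does not help the other side, since that item belongs to the diary and follows its schedule.

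Two further points stand. The Schedule of Activities is not shown and some text beside the diary schedule is redacted, so another symptom assessment in the off-diary weeks cannot be ruled out. And the study ended early, so a protocol edit cannot recover data.

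**Conclusion.** The concern holds in a limited form. The reason given for excluding seven symptoms from AE reporting fails for at least 16 of the 40 treatment weeks (40%), all after Week 12, and for the 30 days after Visit 8. In those periods a listed symptom judged unrelated and no more severe than expected is recorded neither as an AE or SAE nor in the diary. Section 12.4.2 carries the exclusion through to hospitalised cases.

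There is no gap in Weeks 1-12, the scheduled 4-week blocks or the RWP. The primary and secondary efficacy endpoints use only those periods and are not affected. A reader should not infer that all gastrointestinal symptoms go unrecorded in the off-diary weeks, or that the rates in the TEAE tables are wrong by a known amount; the number of events lost cannot be worked out from the documents.

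The count of 16 assumes that Visit 6 lies in Weeks 28 to 36; any other week raises it. The conclusion also assumes that no unseen assessment records these symptoms between diary blocks.

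**What to change.** **In protocol Section 12.4.1** (to correct the record, or for reuse of the text in another study):

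1. Name the DGSSD in place of the DGSSS.
2. Limit the exclusion to scheduled diary periods: Weeks 1-12, the 4-week blocks before Visits 5, 6 and 7, and the RWP. Tie it to the schedule, whether or not an individual entry was completed, so that AE status does not depend on diary compliance.
3. State that new or worsened occurrences outside those periods, including after Visit 8, are recorded as AEs regardless of judged relationship.
4. Reconcile the seven-symptom bullet with the exacerbation and more-severe-than-expected provisions of the same section.

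**For data already collected**, footnote the TEAE tables planned in SAP Section 11.1. The footnote should say that these seven terms were excluded by rule unless judged possibly related or more severe than expected, that at least 16 of the 40 treatment weeks had no scheduled diary, and that the rates shown are therefore not observed incidence.

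**Cost.** A short change to one section and a table footnote, with no new visit or procedure. The downside is more non-serious gastrointestinal AE entries in off-diary periods, and rates for these terms that must be read by diary period. With the study terminated, the footnote is the part that still changes what readers see.
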